[figure not shown]

## Background

Dietary factors are the most important determinants of health in Sweden, and cardiovascular disease is still the leading cause of death in the Western world. Dietary advice is offered less in Swedish primary health care compared with e.g. the USA, and the attitude towards preventive healthcare varies greatly among Swedish GPs, despite many patients in primary care having an elevated cardiovascular risk. The Swedish National Board of Health and Welfare recommends that care providers offer “Kvalificerat rådgivande samtal”, an extensive and theory-based counselling, to all patients with unhealthy eating habits (approximately 20-25% of the Swedish population), especially to patients with elevated cardiovascular risk. Such interventions however demand resources not readily available in clinical practice, and require time, theoretical knowledge in nutrition, and skills in communication e.g. Motivational Interviewing or Cognitive Behavioral Therapy.

Previous studies of lifestyle interventions in primary care have demonstrated only modest effects on LDL cholesterol (0.07-0.16 mmol/L) after 6-12 months, with greater effects after more intense interventions. However, no clear advantage has been demonstrated for dietary counseling by a dietitian compared with self-help resources. Written dietary advice provide the advantage of being simple, objective and reproducible, without being costly or time-consuming. Detailed advice regarding foods that affect blood lipoproteins could also provide individually tailored, person-centered care; in which the patient becomes responsible for the dietary changes he/she wants to pursue. The advice could also contain elements of motivational strategies, in order to increase long-term compliance. Another opportunity is providing personal feedback after three weeks' intervention, as most dietary effects on lipoproteins reach a new steady state after 13-14 days, and three weeks is often considered the least time required for attaining new habits (although more recent research indicates it often takes longer). Personal feedback has provided little or no effect on lipoproteins in previous studies, but as genetic factors and previous dietary habits induces individual differences in responsiveness to dietary changes, this could still be relevant in order to increase long-term compliance, especially for those individuals who get a clear beneficial response.

If such written advice would prove effective not only in the short term, it should be a cost-effective compared with other alternatives and possible to reproduce and implement in Swedish and international primary care. The food choices that lower LDL cholesterol accord well with Swedish and international guidelines for prevention and care of the major non-communicable diseases, e.g., cardiovascular disease, overweight and obesity, diabetes and cancer. Thus, the present study could make available a novel tool in clinical practice, increase access to effective lifestyle counseling and improve patients' diet, even beside effects on blood lipoproteins.

## Purpose

The main purpose is to investigate whether written dietary advice with individual written feedback can affect blood lipoproteins in the short-term (3 weeks) and medium-term (6 months).

## Specific aims

- What effect does written dietary advice have on LDL cholesterol (primary outcome) and other lipoproteins and risk factors (secondary outcomes) after 3 weeks and 6 months, compared with a control group?
- What proportion of individuals achieve a  $\geq 10\%$  reduction in LDL cholesterol from baseline, after 3 weeks and 6 months?
- In the group of responders ( $\geq 10\%$  reduction in LDL cholesterol from baseline), what is the effect after 3 weeks and 6 months?
- Is double sampling of LDL cholesterol required in clinical practice, i.e., how many would be misclassified as responders/non-responders if only one sample was taken at 3 weeks and 6 months?
- How does the intervention's cost compare with estimated future health care savings, as estimated per mean LDL cholesterol reduction, and per individual reaching  $\geq 10\%$  reduction in LDL cholesterol at 6 months?
- Which food choices are associated with reductions in LDL cholesterol in practice?
- What are the reasons given for wanting to reduce LDL cholesterol? Is there any association between reasons given and effect on LDL cholesterol?

## Methods

The study will be carried out at Svärdsjö Primary Health Care Centre, during May 2018 to April 2019, as a pragmatic randomized controlled trial. Participating patients will be recruited by local advertisement at the clinic, in the nearby society, in the local advertisement bulletin and local social media groups. Inclusion criteria are: patients listed at the health care centre, wish to improve blood lipoproteins, ages 18-99 years. Exclusion criteria are: drugs affecting lipid metabolism (statins, ezetimibe, fibrates, PCSK9 inhibitors, neuroleptics, cortisone, amiodarone, estrogen, progesterone, testosterone, cyclosporin, tacrolimus, loop diuretics, protease inhibitors and anti-convulsants, whereas beta-blockers, tiazid-diuretics and SGLT2 inhibitors are accepted at stable use), malignant disease, extreme diet (vegan diet, strict low-carbohydrate diet, other weight-loss diet), disturbed metabolism e.g. untreated hypothyroidism or hyperthyroidism, dementia or inability to understand written Swedish instructions, other participant from same household, employment at the health care centre.

The participants will be block randomized after providing oral and written informed consent to either active intervention or control group (blind to researchers, personnel and participants at study start). If more than one potential participant belong to the same household, only one will be included in the study (by coin toss). All participants will receive an opaque envelope,

provided by an external source that construct the randomization sequence (Uppsala Clinical Research Center). The envelopes contain one double-sided A4 paper containing written dietary advice and some motivational strategies: “It's great that you want to improve your blood lipids! What are your three main reasons that you want to improve your blood lipids? What food choices suit you? How low can you go?” and a table in which participants are instructed to mark each day they have performed specific dietary changes. The intervention group receive detailed information on which food choices that have been demonstrated to beneficially affect LDL cholesterol, in accordance with current dietary recommendations and a recently performed systematic review of the literature (unpublished data). The control group will receive corresponding information, but instead on which food choices are known to reduce fasting triglycerides – advice neutral for LDL cholesterol (and vice versa).

Blood samples will be drawn on days -3, 0 (start of intervention), 18, 21, 180 and 183 (Figure 1). Days -3, 18 and 180, only LDL cholesterol will be analyzed, in order to get double samples three days apart. This reduces the biological variability of LDL cholesterol and thus reduces the required study size, and increases the precision of individual feedback. Days 0, 21 and 183, height (day 0 only), weight, waist circumference and blood pressure will be measured according to local routines and fasting blood samples will be drawn, including LDL cholesterol, total cholesterol, HDL cholesterol, triglycerides, apo B, apo AI, glucose, HbA1c, ALAT, as well as three 4 ml blood samples (whole blood, serum, plasma) to be frozen in -70 °C for future analyzes. Such analyses are not predetermined but may include genetic analyses, lipoprotein subfractions, lipoprotein(a) or serum PCSK9. At day 0, also TSH will be analyzed, in order to identify any unknown disturbances of thyroid function. If TSH is not between 0.1-8.9 mIU/L, the individual will be excluded from the study.

After day 21, participants will receive a standardized written letter containing results from the lab tests and personalized feedback depending on whether their LDL cholesterol has not improved ( $\leq 0\%$ ), improved little (0.1-9.9%), or clearly improved ( $\geq 10\%$  reduction). The control group will receive a letter similar to intervention group, but with effects on triglycerides replacing LDL cholesterol. The effects on triglycerides in control vs intervention groups will also be analyzed as a secondary outcome. However, LDL cholesterol is the surrogate marker most clinically useful and is considered causally related to atherosclerosis development. After day 183, all participants will receive another letter containing results from blood samples and the other groups' dietary advice. Further blood or other analyses will however not be offered as part of the study. In order to compensate for increased expenses, extra health care visits and to minimize loss to follow-up, all participants will receive 500 SEK (~50 €) after the final blood samples are drawn, independently of result on blood lipids or how many dietary changes have been made. Participants that are lost to follow-up at 6 months will however not receive this compensation. The participants will not receive any food items or any other lifestyle advice, in order to make the study environment as similar to clinical practice as possible.

Blood samples will be analyzed at Falu Lasarett using standard routines, during the same day or be kept cool and analyzed the following day, if the sample is drawn in the afternoon. LDL cholesterol is measured in plasma using direct method (P- LDL-Kolesterol SWE05408).

### **Statistical analyses**

Based on previous randomized intervention studies of dietary fat quality and effects on lipoproteins, at least n=222 participants are required (for alpha = 0.05 and beta = 0.10) to detect an effect in LDL cholesterol of 0.175 mmol/L (~5%), which is an effect slightly exceeding that in most previous studies, parallels within-individual day-to-day variation (at double sampling), and has some clinical significance. This calculation takes into account a 20% loss to follow-up in the intervention group and a contamination effect of 5% in the control group.

The results will be analyzed according to intention-to-treat principle. Missing data at follow-up will be handled by imputing the baseline value. For LDL cholesterol, the mean value of the double analyses at days -3/0, 18/21 and 180/183 will be used. The CV of the biological variation will thus be decreased from 7 to 5%. Between-group comparisons for effects on all outcomes will be performed as a generalized linear model (GLM) in SPSS software, adjusted for factors *a priori* considered likely to modify effects (baseline values, BMI, age and sex). As sensitivity analyses, also unadjusted, non-parametric testing (Mann-Whitney U-test) will be performed. P<0.05 will be considered as statistically significant.

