Statistical analysis plan (SAP)

Section 1. Administrative information

1a. Title, registration, versions and revisions

Full study title: Effectiveness of Written Dietary Advice on Lipoproteins - a Pragmatic Randomized Controlled Trial

Acronym: MYDICLIN

1b. Clinicaltrials.gov identifier: NCT03528252

2. SAP version: 1.4, 2019-04-18

3. Protocol version: Research plan version 18-09-20

4. SAP revisions: No major revisions.

5. Roles and responsibility

Author: [name]^{1,2}

Principle Investigator: [name]^{1,2}

Affiliations:

- 1. Unit for Clinical Nutrition and Metabolism, Deptartment of Public Health and Caring Sciences, Uppsala university.
- 2. Center for Clinical research Dalarna

6. Signatures:

I the undersigned, certify that I have read this SAP and approve it as adequate in scope of the main analyses of MYDICLIN.

6. Author and principle investigator

Name: [name]

Date: 2019 - 04 - 18

Section 2. Introduction

7. Background and rationale

Dietary factors are of major importance for public health, but effective means are lacking, to improve dietary habits of patients in primary care. This pragmatic trial aims to investigate whether detailed written dietary advice may be an effective way of improving blood lipoproteins in a Swedish primary care setting.

8. Objectives

The main purpose is to investigate whether written dietary advice with individual written feedback can affect blood lipoproteins in the short-term (3 weeks) and medium-term (6 months).

Specific aims

- What effect does written dietary advice have on LDL cholesterol (primary outcome) and other lipoproteins and risk factors (secondary outcomes) after 3 weeks and 6 months, compared with a control group?
- What proportion of individuals achieve a ≥10% reduction in LDL cholesterol from baseline, after and 6 months?
- In the group of responders (≥10% reduction in LDL cholesterol from baseline), what is the effect after 3 weeks and 6 months?
- Is double sampling of LDL cholesterol required in clinical practice, i.e., how many would be misclassified as responders/non-responders if only one sample was taken at 3 weeks and 6 months?
- How does the intervention's cost compare with estimated future health care savings, as estimated per mean LDL cholesterol reduction, and per individual reaching ≥10% reduction in LDL cholesterol at 6 months?
- Which food choices are associated with reductions in LDL cholesterol in practice?

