P<0.05 will be considered as statistically significant for primary outcomes. For secondary outcomes, significance testing is not as essential as they are mainly hypothesis generating.

17. Adjustment for multiple analyses

The primary outcome is change in LDL cholesterol at 3 weeks and 6 months. The power calculations have been performed for between-group differences at 6 months and this analysis is considered the primary outcome of the study. Thus, no adjustment for multiple analyses will be performed.

18. Confidence intervals

N/A.

Adherence and protocol deviations

19a. Definition of adherence to the intervention

Being randomized and completing the trial (day 183) is considered as sufficient for adherence. For the visit at 3 weeks, no more than 2 days' deviation from protocol will be allowed. For the visit at 183 days, no more than 2 weeks' deviation will be allowed.

19b. Description how adherence will be presented

No specific information on adherence will be presented, besides no. of participants randomized and completing the trial at 3 weeks and 6 months, and no. excluded before and after randomization, with reasons.

19c. Definition of protocol deviations

Deviations from time schedule. Failing to be overnight fasting at time points 2, 4 or 6.

19d. Description of which deviations will be summarized

In cases in which blood samples are taken on the wrong day, the no. of deviations and number of days' deviation from protocol will be reported for each time point. Also, the number indivduals who failed to be completely fasting at time points 2, 4 and 6 will be given.

20. Analysis populations

Study populations will be analyzed according to intention-to-treat principles.

Section 5. Trial Population

21. Screening data

N/A (not collected).

22. Eligibility criteria

Inclusion criteria: patients listed at the health care centre, wish to improve blood lipoproteins, ages 18-99 years.

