For LDL Cholesterol baseline (BL) values will be calculated as the arithmetic mean of values at day -3 and day 0 [(d-3+d0)/2], similarly, values at 3 weeks will be calculated as the arithmetic mean of values at days 18 and 21 [(d18+d21)/2] and values at 6 months will be calculated as the arithmetic mean of values at days 180 and 183 [(d180+d183)/2].

For all continuous variables, absolute change from baseline (Δ) will be calculated at 3 weeks and 6 months as [Δ = 3w - BL and 6m - BL]. Relative change from baseline (% Δ) will be calculated as [% Δ = (3w - BL)/BL and (6m - BL)/BL].

As a sensitivity analysis, variables in the GLM with non-normal distribution will be log transformed (otherwise, no transformations will be performed).

Analysis methods

27a. Analysis methods and presentation of results

Between-group differences for change from baseline (Δ) in continuous variables will be significance tested using a general linear model (GLM). For LDL cholesterol, the results will be presented as a figure with boxplots displaying values at BL, 3 weeks and 6 months for each group. Also, a boxplot of Δ -values at 6 months will be presented for each group. The results will be given in a table format, displayed as mean±SD change from baseline, and P-values for difference between groups.

Difference in mean change from baseline in LDL cholesterol (and triglycerides for control group) between 21 and 18 days and 183 vs. 180 days will be analyzed with t-tests.

Secondary outcome no. 4 (success rate) i.e. the no. and proportion of individuals that achieve a $\leq 0\%$, >0 to <10% or $\geq 10\%$ reduction in LDL cholesterol from baseline will be analyzed by logistic regression, adjusted for age, sex and baseline BMI. No. of individuals that develop impaired fasting glucose will be compared between groups with Fisher's exact test (unadjusted).

Secondary outcome no. 8 (effective food choices) will be analyzed and presented as linear regressions between number of X:s for food choices 1-13 (and the total number of X:s) and change in LDL cholesterol (or Triglycerides within Control group) at 3 weeks and 6 months.

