Further, subgroup analyses will be performed in young (<65 years) vs elderly (65+) individuals, in order to establish whether results are homogenous in these subgroups, for guidance of future studies.

28. Missing data

When data are missing due to loss to follow-up, baseline values will be imputed. If only one time point 3 or 5 is missing (LDL cholesterol at d18 or d180), the mean LDL

cholesterol value will instead be assumed to be the exact value at time point 4 or 6 (d21 or d183).

29. Additional analyses

For possible future analyses (see 26a. secondary outcomes), analyses will be performed with similar methods as other continuous/categorical variables.

30. Harms

Reported adverse effects (if any) will be described in text or table format, depending on the outcome. No serious adverse effects are expected and severity will not be summarized separately.

31. Statistical software

IBM SPSS Statistics 25 will be used for all analyses.

32. References

Data management plan, standard operating procedures, dietary advice, food records and study letters will be stored separately and not provided at trial registry during the study. No statistical master file has yet been created and public access will not be granted.

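### The baseline-imputation rule has no exception for the within-arm food-choice analyses, so a lost participant who has a food table enters them with a fabricated change of exactly 0

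*Protocol*

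**What the plan says.** The protocol's Statistical analyses section adopts intention to treat and adds: "Missing data at follow-up will be handled by imputing the baseline value". SAP 28 says: "When data are missing due to loss to follow-up, baseline values will be imputed". Its one exception is narrow: "If only one time point 3 or 5 is missing (LDL cholesterol at d18 or d180"), the later sample of the pair stands in for the mean. SAP 20 gives a single population: "Study populations will be analyzed according to intention-to-treat principles". SAP 26c says that "absolute change from baseline (Δ) will be calculated at 3 weeks and 6 months as" the follow-up value minus the baseline value.

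One of the listed aims (SAP 8) asks: "Which food choices are associated with reductions in LDL cholesterol in practice". SAP 27a answers it, as secondary outcome no. 8, with "linear regressions between number of X:s for food choices 1-13 (and the total number of X:s) and change in LDL cholesterol", or change in triglycerides within the control group, at 3 weeks and 6 months. SAP 27b leaves these regressions unadjusted. The X:s come from "a table in which participants are instructed to mark each day they have performed specific dietary changes" (Protocol, Methods). SAP 27f compares X:s between responders and non-responders within each arm, at 3 weeks and again at 6 months.

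Neither document gives the food-choice analyses their own analysis set. Neither states the length of the table, when it is returned, or how an unreturned table is counted.

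**The concern.** Imputing baseline may be defended as cautious in a randomised comparison. That defence does not carry over to an association inside one arm. There, the imputed 0 is paired with a count of X:s that the participant really made, and the pair says nothing about what the food did to that person's LDL.

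The clearest case is a participant whose table is already in hand and who is then lost before day 180. The X count is genuine and the 6-month change is invented. Depending on how leavers marked, such points either flatten a real association or create one for a food with no effect. The plan does not say which situation applies. At stake is the answer to a listed aim: which foods go with lower LDL in practice.

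**Working it through.** **1. The plan's own figure.** The documents give no figure for the food-choice regressions. The SD of LDL change is not stated either, so the sample size of 222 can only be back-solved, using n per arm = 2(1.96 + 1.2816)² × SD² / 0.175².

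- SD 0.30 gives 61.8, so 62 per arm. Then 62/(1 − 0.20 − 0.05)² = 62/0.5625 = 110.2, so 111 per arm and 222 in total.
- With no inflation, 222 implies an SD of about 0.40.

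The SD is therefore an assumption. The range 0.3–0.5 mmol/L is shown below.

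**2. The imputed change.** With follow-up set to baseline (BL), Δ = BL − BL = 0 and %Δ = 0. That falls in the no-reduction category, so the participant is a non-responder whatever they ate.

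**3. Effect on the slope.** Let a share d be lost, with change 0. Subscript c denotes completers and l the lost; V is the variance of X, b the completers' true slope and Ȳc their mean change. Then

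slope = [(1 − d)·b·Vc + d(1 − d)(X̄c − X̄l)·Ȳc] / [(1 − d)·Vc + d·Vl + d(1 − d)(X̄c − X̄l)²].

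Inputs:
- d = 20% (the protocol's loss figure for the intervention group), with 10% and 5% as assumptions.
- Ȳc = −0.175 mmol/L. This borrows the between-group detectable effect as a within-arm mean change, which is an assumption.
- Completers' X scaled to mean 2 and SD 1 (assumption).
- Leavers have the same X distribution, half the mean (variance 1), or zero X:s (variance 0).

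Examples at d = 20%:
- Same X, b = −0.10: (0.8 × −0.10)/(0.8 + 0.2) = −0.080.
- Half X, b = 0: (0.16 × 1 × −0.175)/(0.8 + 0.2 + 0.16) = −0.028/1.16 = −0.024.
- Zero X, b = 0: (0.16 × 2 × −0.175)/(0.8 + 0.64) = −0.056/1.44 = −0.039.

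| Loss | True slope | Same X | Half X | Zero X |
|---|---|---|---|---|
| 20% | 0 | 0 | −0.024 | −0.039 |
| 20% | −0.10 | −0.080 | −0.093 | −0.094 |
| 10% | 0 | 0 | −0.014 | −0.025 |
| 10% | −0.10 | −0.090 | −0.097 | −0.096 |
| 5% | 0 | 0 | −0.008 | −0.015 |
| 5% | −0.10 | −0.095 | −0.099 | −0.098 |

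If Ȳc = 0, a food with no effect keeps slope 0 in every column.

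**4. False positives for a food with no effect.** Simulation of one arm of 56 (113 participants, 1:1), 20,000 runs, two-sided 5% test of the slope, Ȳc = −0.175. Entries are for residual SD 0.3 / 0.4 / 0.5.

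| Loss | Same X | Half X | Zero X | Lost excluded |
|---|---|---|---|---|
| 20% | 5% throughout | 9 / 7 / 6% | 22 / 13 / 9% | 5% throughout |
| 10% | 5% throughout | 6 / 5 / 5% | 10 / 7 / 5% | 5% throughout |
| 5% | 5% throughout | about 5% | about 4–5% | 5% throughout |

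A second set-up used 13 foods with counts over an assumed 21-day table (mean 10.5, SD 6, correlation 0.3), SD 0.30 and 20% loss. If marking stops part-way, it gives 9–10% per food and 12–14% for the total count. If all leavers are scored zero, it gives 21% and 30–31%.

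**5. Timing of loss.** In that second set-up, split the 11 losses (20% of 56) between early leavers scored zero and later leavers with complete tables. With 3 early and 8 late, false positives are 5.0% per food and 4.8% for the total. With 5 early and 6 late, they are 6.8% and 7.6%. The split is an assumption.

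**6. Measured values only.** At 20% loss and SD 0.3, a true slope of −0.10 is recovered as −0.100, and a true slope of 0 gives about 5% false positives. This holds if loss is unrelated to the relation between X:s and LDL.

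**The case against.** The strongest reply is that entry is inferred. No sentence says that imputed changes go into the food-choice regressions. In the protocol, the imputation rule sits in a paragraph about between-group comparisons. An X count has no baseline value, so the rule cannot supply one: a participant with no table has no regressor and drops out harmlessly. This stands for participants without a table. It does not cover someone whose table was returned before the loss. For that person the rule, the single population and the absence of any exemption lead to an imputed 0.

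A reader might go further and infer that roughly one food in five would be falsely positive. That needs unreturned tables scored as zero, which neither document says, and all losses to come early or with no table returned. It also needs an SD near 0.30, which the plan does not state. SAP 27a, for outcome no. 9, expresses X:s as a proportion of those possible. This hints that unmarked days may count as unmarked, but it is not a rule for missing tables.

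A reader might also infer that dropout by itself distorts all 13 foods. It does not. A food with no effect is untouched if leavers marked like completers or the arm's mean change is 0. For a real effect the two distortions can nearly cancel (−0.10 becomes −0.094).

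It is also fair that SAP 16 calls secondary outcomes mainly hypothesis generating, and that counting leavers as non-responders is a common convention. Both points lower the weight of the issue. Neither makes an imputed 0 informative about a food.

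**Conclusion.** The point holds as a minor one. Applied as written, the imputation rule puts lost participants who have a food table into the within-arm analyses with a change of exactly 0, always as non-responders.

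The flattening by the loss fraction is exact when leavers' X:s resemble completers'. The spurious slope depends on leavers having fewer X:s and completers' LDL falling. Its size rests on assumed values for loss, mean change, residual SD and the distribution of X:s. At 20% loss the rate is about 6–10% per food with half or part-way marking, and 9–22% under zero coding. At 5–10% loss, or when most losses come after the table is complete, it is mostly close to 5%; the exception is zero coding at 10% loss and SD 0.3, at 10%. The randomised comparisons, including the primary outcome, are not affected.

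**What to change.** Add to SAP 27a (outcome no. 8) and 27f: food-choice analyses, and comparisons of X:s between responders and non-responders, include only participants with a measured LDL (or triglyceride) value at that time point and a returned food table; unreturned tables are treated as missing, not as zero X:s. The version with imputed values may be kept as a sensitivity analysis. The intention-to-treat set stays for all between-arm comparisons.

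The cost is one sentence and a few participants, none with a real outcome value or none with a table, leaving an exploratory analysis. The restricted analysis assumes that loss is unrelated to the relation between X:s and LDL, and the report should say so.
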